
Criteria for Patient Discontinuation from Study
	
Patients are free to withdraw from the study at any time, without prejudice to their continued care.
 
Patients may be discontinued from the study at any time if clinically significant out-of-range laboratory values, clinically significant abnormal findings on physical examination, or intolerable TEAEs put the patient at additional risk, as judged by the investigator. Patients experiencing TEAEs considered to be study drug-related and not tolerated by the patient will be discontinued from the study. Patients must be discontinued from the study if the absolute neutrophil count is less than 1000/mm³ (or 1.0 x 10E9/L). A complete list of reasons for patient discontinuation is located in Section 4.3 of the protocol.
 
The Study Sponsor (Biotie Therapies, Inc.) has the right to terminate the study at any time.
 
All patients who discontinue prematurely from the study will be requested to return to the study site as soon as possible to complete the safety and efficacy evaluations outlined for an Early Termination Visit in the Schedule of Events/Evaluations (Table 1). The Early Termination Visit should be done while the patient is taking IMP, if possible. After Early Termination, the patient will also be asked to return for a Safety Follow-Up Visit to be scheduled 28 days after the last dose of IMP, unless the Early Termination Visit itself occurred 28 or more days after the last dose of IMP.
 
All TEAEs will be followed until resolution, return to Baseline level, or stabilization.

PROTOCOL SYNOPSIS

Sampling for Tozadenant Plasma Drug Concentrations
	
Pharmacokinetic (PK) blood samples for determination of plasma tozadenant concentration will be collected at the Week 2 study visit. [REDACTED] blood sample will be collected at the most convenient time during the visit (“Sparse PK Sampling”). [REDACTED] PK blood samples may be collected (“Expanded PK Sampling” - additional details are provided in Appendix 15.9). On the morning of the Week 2 visit, participating subjects will refrain from taking their 120 mg IMP dose until after collection of a predose/trough PK sample. [REDACTED]

Sample Size Justification
	
Approximately 645 patients will be screened, assuming a 30% screen failure rate, to enroll 450 patients.

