25. Patients with moderate to severe hepatic or renal impairment.
26. 
27. **Patients with absolute neutrophil count less than 2000/mm³ (or 2.0 x 10E9/L) at screening.**

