4.3.2 Definite Criteria for Withdrawal from Study

Patients must be discontinued from the study if any of the following events occur:

1. Patient develops an illness that would interfere with his or her continued participation.
2. Patient withdraws his or her consent.
3. Confirmation of patient pregnancy during the study, as evidenced by a positive pregnancy test.
4. The Sponsor/Sponsor's designee or a regulatory agency requests withdrawal of the patient.
5. The Sponsor or a regulatory agency terminates the study.
6. Patient has active suicidality since last visit as indicated by a positive response ("Yes") to either Question 4 or Question 5 of the C-SSRS, or reports any suicidal behavior since their last C-SSRS assessment. The patient should be referred immediately to a Mental Healthcare Professional.
7. The patient has a QTcF interval consistently ≥ 500 msec and/or a QTcF interval consistently increased by ≥ 60 msec compared to the average baseline QTcF interval. The average baseline QTcF interval is defined as the average of the three QTcF interval values obtained at Visit 2. Fridericia's method must be used for correction of QT intervals.
8. Investigators must follow guidelines provided related to monitoring hepatic parameters in relation to investigation guidelines and stopping rules. The following necessitate immediate cessation of dosing with IMP:
 - a. Patients with ALT or AST $>8x$ ULN.
 - b. Patients with ALT or AST $\geq 3x$ ULN and co-existing total bilirubin $\geq 2x$ ULN*.
 - c. Patients with ALT or AST $\geq 3x$ ULN who exhibit a temporally associated fatigue, nausea, vomiting, right upper quadrant pain or tenderness, fever (without clear alternative cause), rash or eosinophilia ($>5\%$).

*Patients with significant elevation of alkaline phosphatase (ALP; ALP >2x ULN) indicating biliary obstruction to be discussed with the Medical Monitor.

9. Patients noted to have an elevated BP post-baseline, with a supine systolic BP \geq 160 mmHg and/or a diastolic BP \geq 100 mmHg that is present at 2 consecutive post-baseline study visits.
10. Patients have concomitant surgical intervention for PD, including but not limited to deep brain stimulation.

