11. **Patients with an absolute neutrophil count less than 1000/mm³ (or 1.0 x 10E9/L).*** **Following study drug discontinuation, these patients will require weekly hematology measurement until the WBC and/or ANC returns to 75% of the baseline value (Visit 2). Assess for adverse events and concomitant medication changes and record as an unscheduled visit. Discuss with medical monitor to assure that the patient is discontinued from study drug and that the appropriate follow up safety measures are taken.**

*Any patient experiencing a decline in absolute neutrophil count (ANC) and/or white blood cells (WBC) by 50% from baseline (Visit 2) will require weekly hematology measurement until the WBC and/or ANC returns to 75% of the baseline value. The patient will continue with dosing during the weekly hematology follow-up. Assess for adverse events and concomitant medication changes and record as an unscheduled visit. If the WBC and/or ANC returns to 75% of baseline, the patient should return to routine evaluations as outlined in the Schedule of Events/Evaluations. Discuss with medical monitor.

All patients who discontinue prematurely from the study will be requested to return to the study site as soon as possible to complete the safety and efficacy evaluations outlined for an Early Termination Visit in the Schedule of Events/Evaluations (Table 1) and in Section 6.2.20. The Early Termination Visit should be done under IMP treatment, if possible. After Early Termination, the patient will also be asked to return for a Safety Follow-Up Visit to be scheduled 28 (\pm 3) days after their last dose of IMP, unless the Early Termination Visit itself occurred 28 or more days after the last dose of IMP (see Section 6.2.19).

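### The note attached to the ANC <1000/mm³ withdrawal criterion (Protocol 4.3.2, criterion 11) says dosing continues and makes no exception for patients who meet that criterion

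*Protocol*

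**What the plan says.** Protocol 4.3.2 opens with "Patients must be discontinued from the study if any of the following events occur". Criterion 11 in that list is an ANC below 1000/mm³. Its own text requires weekly haematology after study drug is stopped, until the counts recover to 75% of the Visit 2 value. It then adds: "Discuss with medical monitor to assure that the patient is discontinued from study drug". The synopsis, under the criteria for patient discontinuation, states the same rule without any note: "Patients must be discontinued from the study if the absolute neutrophil count is less than" 1000/mm³.

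The 1000/mm³ threshold in criterion 11 carries an asterisk. The note it leads to covers any patient with a 50% decline in ANC and/or white blood cells (WBC) from Visit 2. It asks for weekly haematology until recovery to 75% of baseline, followed by a return to the routine schedule, and for discussion with the medical monitor. On dosing it says: "The patient will continue with dosing during the weekly hematology follow-up".

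The entry floor is exclusion 27 in section 4.2: "Patients with absolute neutrophil count less than" 2000/mm³ are excluded, and the criterion names Screening as the time of the test.

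**The concern.** The asterisk sits on the stopping threshold, so a reader who follows it will naturally take the note as qualifying that threshold. The note applies to any patient with a halved count, has no lower bound on ANC, and does not say what happens to a patient who is also below 1000/mm³. Taken literally, such a patient must be discontinued under the criterion and keeps taking drug under its note.

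Some neighbouring text makes the two paths look alike. Both use weekly haematology and the same 75% recovery mark. Tables 1.1 and 4.1 have a single weekly-monitoring column that refers back to 4.3.2. The reduced unscheduled visit for weekly haematology (6.2.21.1) omits the drug collection and last-dose questions asked at other unscheduled visits, so that visit has no built-in check on whether dosing has stopped.

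Two things are at stake across approximately 120 sites. The first is consistent handling of patients with a low neutrophil count. The second is the safety data: if sites read the rule differently, discontinuations and drug exposure after a low count would partly reflect each site's reading.

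**Working it through.** The plan gives no figure to reproduce here. The check is whether the two triggers can be met by the same patient, and for which counts.

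**Inputs**
- Criterion 11 (4.3.2 and synopsis): ANC < 1000/mm³.
- Note to criterion 11 (4.3.2): a fall of 50% from Visit 2 in ANC and/or WBC, read here as 50% or more.
- Exclusion 27 (4.2): ANC at least 2000/mm³ at Screening.

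**Formula.** Let B be the Visit 2 ANC and A a later ANC.
- Percentage fall = 100 × (1 − A/B).
- Criterion 11 is met when A < 1000.
- The note is met through ANC when A ≤ B/2.
- Both are met when A < 1000 and A ≤ B/2.

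**Case 1: B ≥ 2000.** Then B/2 ≥ 1000, so any A < 1000 is also below B/2. The smallest possible fall, in whole counts, is 999 from 2000: 100 × (1 − 999/2000) = 50.05%. The overlap is complete.

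**Case 2: B < 2000.** Then B/2 < 1000, and both rules apply only for A ≤ B/2. Counts above B/2 and below 1000 meet criterion 11 without a 50% fall in ANC. For example, 950 from 1800 is 100 × (1 − 950/1800) = 47.2%.

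| Visit 2 ANC (B) | B/2 | Fall at A = 999 | Both rules | Criterion 11 only | Note only |
|---|---|---|---|---|---|
| 1600 | 800 | 37.6% | up to 800 | 801–999 | none |
| 1800 | 900 | 44.5% | up to 900 | 901–999 | none |
| 1900 | 950 | 47.4% | up to 950 | 951–999 | none |
| 2000 | 1000 | 50.05% | up to 999 | none | exactly 1000 |
| 3000 | 1500 | 66.7% | up to 999 | none | 1000–1500 |
| 4000 | 2000 | 75.0% | up to 999 | none | 1000–2000 |

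The table uses the ANC trigger only. A 50% fall in WBC also triggers the note. It can do so alone, with ANC at or above 1000, or it can bring a patient in the criterion-11-only column into the overlap.

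**Can B be below 2000?** As worded, yes. Exclusion 27 tests ANC at Screening, up to 6 weeks before Visit 2. Section 6.2.2 says in general terms that eligibility must also be met at Baseline, which could be read as carrying the floor forward. But criterion 27 names only Screening, Visit 2 blood is drawn at the visit where drug is assigned (6.2.3.1 and 6.2.3.2), and the eligibility check in 6.2.3.3 does not list the haematology result.

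**The case against.** The strongest reply is that the section already describes two tiers: a halved count is monitored weekly on drug, and a count below 1000/mm³ means stopping and then weekly monitoring. Much of the text supports this.

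- Criterion 11 has its own weekly monitoring after drug is stopped. That would be redundant if the note governed the same patients.
- The note ends with a return to the routine visit schedule, which fits only a patient still in the study.
- The note has a population of its own: ANC falls that stay at or above 1000 (for example 1000–2000 from 4000) and falls in WBC alone.
- Discontinuation below 1000 appears under a mandatory heading and again in the synopsis. Both paragraphs involve the medical monitor, and in criterion 11 the stated purpose of that contact is to make sure drug has been stopped.

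This stands as the likely intent. It also answers one stronger inference, that the protocol has no effective stop below 1000/mm³ or that the note overrides it. The documents do not support that: the stop is present, repeated and backed by medical-monitor contact, and the note does not claim precedence.

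A second tempting inference is that every patient who falls below 1000 must also meet the note, because entry requires 2000. That is not guaranteed either, because the entry floor is set at Screening and the note measures from Visit 2.

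What the objection does not remove is the literal conflict. The boundary between the tiers has to be inferred against a sentence that covers any patient and is attached to the stopping threshold itself.

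**Conclusion.** The point holds as a wording conflict in a safety stopping rule, and it should be fixed. For a Visit 2 ANC of at least 2000/mm³, 100% of patients who meet criterion 11 also meet the trigger of a note that tells them to stay on drug. Below 2000 at Visit 2, the overlap through ANC is partial. This rests on reading the note's 50% as 50% or more and on taking the Visit 2 ANC as the reference value, as the note states.

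A reader might go further and treat this as a failure of the protocol's central safety rule. The documents do not rank criterion 11 above the other ten definite criteria. The stop-below-1000 and monitor-at-50% design is not in question here. Nothing in the documents shows that a site has kept, or would keep, dosing such a patient.

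**What to change.** Reconcile the note in 4.3.2 with criterion 11 and the synopsis so that the instruction to discontinue and the instruction to continue dosing cannot apply to the same patient. State which text takes precedence where both triggers are met. The wording should cover both the ANC and the WBC trigger; it then works whatever the Visit 2 ANC. Which rule governs is a clinical decision for the sponsor, and none is proposed here.

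The cost is one clarifying clause, with the synopsis kept in step, and a letter to the sites. If the sponsor judges the change significant, it goes through the amendment route in section 12.4. No visit, sample or analysis needs to change.

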5.0 STUDY TREATMENT(S)

5.1 Description of Investigational Medicinal Product

Table 2: Investigational Medicinal Product

	Tozadenant
Dosage Form:	[REDACTED]
Route of Administration:	Oral
Batch Number:	Will be assigned according to Good Manufacturing Practice (GMP)
Retest Date:	Will be assigned according to GMP

5.2 Treatment(s) to be Administered

Investigational medicinal product is comprised of immediate-release, active tozadenant tablets for oral administration, as described above.

5.3 Packaging

The IMP supplies for this study will be packaged according to current Good Manufacturing Practice (GMP) guidelines and applicable national laws and regulations. Supplies will be packaged in such a way as to protect the products from deterioration during transport and storage. For this study, IMP will be packaged in an open-label fashion in high-density polyethylene bottles containing one hundred (100) 60 mg tozadenant tablets per bottle or fifty (50) 120 mg tozadenant tablets per bottle.

Sites will be supplied with an initial stock that will be monitored by the IXRS, and resupply will be organized throughout the duration of the study in order to ensure sufficient open-label clinical IMP supplies are available onsite.

5.4 Labeling

Supplies of IMP will be labeled in accordance with current FDA and local regulations (and as applicable, International Conference on Harmonisation [ICH] guidelines) regarding Good Clinical Practice (GCP) and GMP, and will include any locally required statements. If necessary, labels will be translated into the local language.

5.5 Handling and Storage Requirements

The investigator is responsible for the safe and proper storage of IMP supplies at the site in accordance with labeling and written storage instructions. From receipt until final disposition (e.g., return shipment to Sponsor's authorized designee), IMP stored by the investigator is to be kept in a secured area with limited access.

[REDACTED] Appropriate storage conditions must be ensured and documented by completion of a temperature log in accordance with local requirements on a regular basis, showing minimum and maximum temperatures reached over the time interval.

In case an out-of-range temperature is noted, it must be immediately communicated to the Sponsor/Sponsor's designee before further use of the IMP. The Sponsor/Sponsor's designee will transmit the out-of-range temperature (copy of the temperature log and duration of the out-of-range temperature, if available) to the Sponsor's Quality Assurance (QA) representative. Based on discussion with the Sponsor's QA representative, the Sponsor/Sponsor's designee will then provide the site with instructions regarding use of the IMP.

The investigator or designee will instruct the patient to store the IMP according to the instructions on the label.

5.6 Dosing Instructions

Eligible patients will be instructed to take the specified number tablets of open-label IMP by mouth BID, in the morning and in the evening preferably at the same time each day.

All patients, upon start of study:	2 tablets (2 × 60 mg tablets), BID OR 1 tablet (1 × 120 mg tablet), BID
If dose reduced at Week 2 or later:	1 tablet (1 × 60 mg tablet), BID
If dose is subsequently increased:	2 tablets (2 × 60 mg tablets), BID OR 1 tablet (1 × 120 mg tablet), BID

The evening dose should be approximately 12 hours after the morning dose. Patients will be instructed to take their morning and evening doses at least 1 hour before or 2 hours after a meal and to refrain from eating for at least 1 hour after dosing. In the event of a missed dose, patients will be instructed to take their next dose of IMP at the normally scheduled time.

5.7 Drug Accountability

A Drug Accountability Form will be used to record IMP dispensing and return information on a by-patient basis and will serve as source documentation during the study. Details of any IMP lost (due to breakage or wastage) or not used at the study site or returned to the Sponsor's authorized designee must also be recorded on the appropriate forms. All clinical IMP supplies and drug accountability and related pharmacy documentation must be made available throughout the study for the Sponsor/Sponsor's designee to review.

The investigator (or designee) is responsible for retaining all used, unused, and partially used clinical IMP supplies until they are returned to the Sponsor's authorized designee.

Periodically during the study and upon completion of the clinical phase of the study, all used, unused, and partially used clinical IMP supplies will be reconciled and returned in their original containers (i.e., bottles) to the Sponsor's authorized designee.

Clinical IMP supplies intended for this study cannot be used for any other purpose than that described in this protocol. The investigator must ensure that IMP is used only in accordance with this protocol.

5.8 Procedures for Monitoring Patient Compliance

After IMP is dispensed, at each subsequent study visit patients must return all used, unused, and partially used clinical IMP supplies. Drug accountability must be done in the patient's presence in order to obtain explanations regarding discrepancies in compliance with the dosing regimen. Drug accountability must be recorded on the Drug Accountability Form. Upon completion of the patient's Visit 8 at Week 52 (or Early Termination Visit, whichever occurs first), the authorized study staff will enter the date of the last dose of IMP taken in the source documents and eCRF to register the end of treatment for that patient.

If a patient is found to be persistently noncompliant (≤ 80 to $\geq 120\%$ of the assigned dose), the Sponsor/Sponsor's designee, in conjunction with the investigator, will make a decision as to whether the patient should be discontinued from the study.

5.9 Concomitant Medications/Treatments

5.9.1 Allowed Anti-PD Medications/Treatments

During this study, patients' concomitant anti-PD medications (i.e., levodopa-containing medication, dopamine agonists, MAO-B inhibitors, anticholinergic agents, amantadine or entacapone) may be adjusted as needed under the investigator's supervision. The optimal dose of open-label tozadenant for each patient will be defined following discussion between the patient and the investigator, taking into account the potential for improvement of disease symptoms and the tolerability profile.

Throughout the study, all anti-PD medications taken by a patient during the study and the reason for their use will be recorded in the source documents and eCRF.

Patients will use their own supply of anti-PD medication throughout the study.

5.9.2 Prohibited Concomitant Medications/Treatments

The following concomitant medications and treatments are prohibited throughout the study:

- Digoxin.
- Surgical intervention for PD during the study.
- [REDACTED]

- Apomorphine, budipine, istradefylline, tolcapone, or [REDACTED]
- Antipsychotics except quetiapine administered at doses of ≤ 100 mg per day and pimavanserin
- Metoclopramide
- Methyldopa
- Amphetamines and ephedra

5.9.3 Other Concomitant Medications/Treatments

During the study, patients are asked to refrain from the use of any concomitant medication without the specific prior approval by the investigator. All medications taken by a patient and the reasons for their use will be recorded in the source documents and eCRF.

Patients taking thyroid medication for hypothyroidism or hyperthyroidism must be on a stable dose for at least 3 months prior to the Baseline Visit.

5.10 Blinding

This study will be open-label.

5.11 Enrollment and Numbering of Patients

During the study, the IXRS will be used for initiating the dispensing of open-label IMP as well as tracking the progression of patients in the open-label phase and ensuring an adequate supply of open-label IMP. The IXRS will also be used to dispense IMP supplies, according to the visit schedule and dose level assigned by the investigator.

6.0 STUDY PROCEDURES BY VISIT

6.1 Overview of Study Procedures

An overview of the conduct of the study, including the timing of study visits and assessments performed, may be found in [Table 1](#) and [Table 1.1](#). Details of disease activity and safety assessment methods can be found in [Section 7.0](#) and [Section 9.0](#), respectively, and in the applicable appendices. Plasma drug concentration assessments are described in [Section 8.0](#). Detailed procedures by visit are provided in [Section 6.2](#).

Note: Laboratory supplies that are needed for protocol-specified tests will be provided by the central laboratory.

Consented patients will be screened for eligibility. During the Screening Period, the patient (and any caregiver that will assist the patient to complete PD diaries during the study) will complete PD diary training and a diary concordance session (see [Section 7.1](#) and [Appendix 15.13](#)) with the site's diary trainer/rater. The patient (and caregiver, as applicable) will review the PD diary training video and receive instruction on how to complete the PD diary, including the definitions of ON and OFF. The definitions of ON and OFF will be reviewed, including ON time according

to dyskinesia categories “without dyskinesia”, “with non-troublesome dyskinesia” or “with troublesome dyskinesia”, with emphasis on the need for the patient to be consistent in their use of the definitions when rating their status in the PD diary during the study.

When instructions appear to have been understood by the patient (and caregiver, as applicable), a PD diary concordance session will be initiated during which the patient and diary trainer/rater will concurrently complete separate training diaries for at least 5 consecutive half-hour intervals (minimum 2.5 hours). During the diary concordance session, the patient must experience both ON and OFF. The 2.5 hour session may be extended, as needed, so that the patient experiences OFF. If the patient is OFF at the beginning of the diary concordance session, they may be administered their next dose of levodopa-containing medication in order to experience ON. When the session is completed, the trainer/rater will review and assess diary concordance between the patient and the trainer/rater. The patient is required to reach at least 80% overall concordance with the trainer/rater including at least 1 OFF interval. If the concordance criteria are not achieved, the trainer/rater will schedule a second PD diary training and diary concordance session within the 6-week Screening Period, unless the patient declines further participation.

Following successful completion of the PD diary training and a diary concordance session, patients/caregivers will be required to complete practice PD diaries on 3 consecutive prespecified days (24-hour periods starting at 6 AM each day). The trainer/rater will telephone the patient to remind them to start keeping the PD diary prior to the start date, to review the ON and OFF definitions, and to answer any questions the patient may have regarding completion instructions.

Practice PD diaries will be returned to the trainer/rater and reviewed with patients/caregivers over the telephone or in person to ensure PD diary completion instructions are fully understood. Patients with invalid practice diaries will be asked by the trainer/rater either to complete a second PD diary training and diary concordance session followed by a repeat 3-day practice diary, or else asked to repeat the 3-day practice diary, depending on the patient’s understanding of the diary instructions. Patients who do not satisfy diary concordance criteria during a second PD diary training and/or who return a second set of practice diaries that are invalid, will be considered screen failures.

Patients who return valid practice PD diaries and who the investigator considers eligible for the study will be scheduled within 6 weeks from the Screening Visit. The patient will be instructed to complete the Baseline PD diary on the 3 consecutive days directly preceding the scheduled Baseline Visit. The trainer/rater will contact the patient prior to the start date to remind them to start keeping the PD diary, to review the ON and OFF definitions, and to answer any questions the patients or caregiver may have regarding completion instructions. The patients will be requested to bring the Baseline PD diary to the Baseline Visit, at which the PD diary will be assessed for validity and to confirm the patient’s eligibility. Patients not meeting the criteria for valid Baseline PD diary completion may be retrained, as described above, and may return for another Baseline assessment within the 6-week Screening Period.

Patients who meet all the entry criteria at Baseline will be assigned IMP using the IXRS and will begin open-label treatment for 52 weeks. The first dose of IMP will be taken at home after the Baseline Visit. Patients will be evaluated at scheduled study visits on Weeks 2, 4, 6, 8, 10, 12, 16, 20, 24, 36, 44, 52, and 56; and will be asked to complete a PD diary on the 3 consecutive days directly preceding visits on Weeks 12, 24 and 52. Prior to each 3-day PD diary completion

period, patients will be telephoned to be reminded to comply with the PD diary instructions. Patients will be requested to bring their PD diary to the scheduled visits. Safety evaluations will be performed at each study visit. At specified visits, patients will be asked to return their IMP dispensed at the previous visit (including all unopened and opened IMP bottles) and to bring their other medications to the visit. Patients will be instructed to have already taken their normally scheduled dose of levodopa and their IMP prior to arriving at the study site in order to have their UPDRS Part III evaluated in the ON state (within approximately 1 to 3 hours after taking their levodopa dose). UPDRS in OFF will not be evaluated. Pharmacokinetic (PK) blood samples will be collected for tozadenant at Week 2 as outlined in [Table 1](#), Schedule of Events/Evaluations. **Patients will also be scheduled for a laboratory draw (hematology measurement only) at Weeks 4, 8, 10, 16, 20 and 44 as outlined in [Table 1.1](#).** All patients completing the study will be scheduled for a required postdose Safety Follow-Up Visit 28 ± 3 days after completion of the 52-week open-label treatment period. In the event of Early Termination, patients will be asked to complete an Early Termination Visit as soon as possible and to return for a Safety Follow-Up Visit 28 ± 3 days after their last dose of IMP, unless the Early Termination Visit itself occurred 28 or more days after the last dose of IMP.

Please refer to the Schedule of Events/Evaluations in [Table 1](#) and [Table 1.1](#) for specific timing of assessments and [Section 6.2](#) for detailed study procedures.

